The proposed 6-mo. pilot trial will compare the feasibility and effectiveness of DPP delivered through Facebook (DPP-FB) or group format delivered remotely by phone conference call (DPP-R) in 30 adults (age ≥ 18 yrs.) with prediabetes. Both interventions will be delivered through the CES, which serves as the community outreach arm of all land grant universities through over 2,900 offices across the U.S. The Kansas State Research and Extension (KSRE) (Kansas version of CES), is well positioned, but underutilized for the delivery of DPP in rural areas. Delivery of DPP by a well-recognized entity, such as the KSRE, may improve the probability of dissemination and long-term program sustainability. Two CES offices serving rural counties in Kansas will be randomized (1:1) to the DPP-FB or DPP-R arms. Our research team will train 2 professional staff from KSRE (with backgrounds in nutrition programming and family consumer science) who will deliver the DPP intervention. Outcomes will include body weight

and moderate-vigorous physical activity assessed at baseline, 3 mos. and 6 mos., participant retention, i.e. weight assessed at 6 mos., program attendance (percentage of 16 sessions attended), and the fidelity of intervention delivery. i.e., the delivery of $\geq 80\%$ of scheduled content as determined by reviewing audio recordings of all DPP sessions. This project will address the following aims:

Primary aim: **Compare weight and MVPA between DPP-FB and DPP-R across 6 mos.** We expect greater weight loss and MVPA in the DPP-R arm compared with the DPP-FB arm.

Secondary aim: **Compare the feasibility of DPP-FB and DPP-R across 6 mos. based on participant retention and program attendance.** We expect greater participant retention and program attendance in the DPP-R arm compared with the DPP-FB arm.

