This study will provide the pilot data necessary to apply for NIH funding to conduct a larger, adequately powered trial comparing the effectiveness of remote and Facebook group delivery of DPP through the KSRE to adults living in rural counties. Compared with DPP delivered in-person, Facebook or remote delivery of DPP eliminates the time and cost burdens of travel to attend behavioral sessions and may increase sessions attendance, which is strongly associated with weight loss success. Demonstrating that remote and Facebook delivery of DPP are at a minimum non-inferior to in-person, may be helpful in weight management providers ability to obtain reimbursement through the Centers for Medicare and Medicaid Services for remotely delivered DPP, which currently reimburses for in-person DPP programs only.

BACKGROUND/SIGNIFICANCE

Diabetes in rural residents. Approximately 72% of adults in the U.S. are overweight or obese of which 9.5% have diagnosed type 2 diabetes (T2D) (1). The prevalence of prediabetes based on fasting glucose or hemoglobin A1C is estimated to be 33.9% in U.S. adults age 18 yrs. and over, and 48.3% in those age 65 yrs and above (2). Approximately 70% of those with prediabetes will eventually develop T2D (3). The burden of diabetes disproportionately impacts the 60 million individuals (19.3% of the U.S. population) living in rural areas where the prevalence of T2D and obesity, a modifiable risk factor for T2D, are higher than their urban counterparts (4). Rural residents experience higher rates of chronic disease included diabetes, metabolic syndrome, cardiovascular disease, have higher coronary heart disease and all-cause mortality and higher rates of disability compared to their urban counterparts (15-19). These health disparities may, in part be, associated with a higher prevalence of obesity in rural (~40%) compared to urban residents (~33%). The proportion of the U.S. population age 65 yrs. and older, where the prevalence of prediabetes is extremely high, is 17.5% in rural areas compared with 13.8% in urban areas. Effective prevention of T2D in rural adults would have a significant public health impact.

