Reimbursement of DPP. The CDC maintains a registry of community organizations that have satisfied requirements for delivery of the DPP program. The CDC recognizes multiple delivery options for the DPP including: in-person, online, distance learning and a combination program. Recognized programs are eligible for cost reimbursement from the Centers for Medicare and Medicaid Services (CMMS); however, only in-person programs are currently eligible for reimbursement. Additional research to evaluate the feasibility and effectiveness of alternative delivery methods such as group video conferencing and Facebook, as we have proposed, will contribute to the knowledge base required to obtain CMMS reimbursement in the future.

INNOVATION

Innovative aspects of this proposal include: 1) Targeting an under-served, at-risk group, i.e., rural residents at risk for T2D, 2) Partnering with Kansas State Research and Extension (KSRE) that is an established and a widely utilized community outreach arm across the state of Kansas, 3) Using existing KSRE infrastructure for intervention delivery in rural communities which may increase the probability of perpetuation and reach of the intervention.

APPROACH

Design overview. The proposed 2-arm trial will compare the feasibility and effectiveness of Facebook or remote-delivery of the DPP in rural adults with prediabetes both delivered through the KSRE. The CES is a non-formal educational program, implemented in the U.S. through each state's designated land grant university, to help people use research-based knowledge to

improve their lives. The KSRE maintains local units which are comprised of single counties or multi-county districts. Two KSRE local units serving rural counties will be identified by our partners at KSRE and randomized to the Facebook or remote delivery arms. Members of the KUMC research team will recruit and consent participants and will train KSRE personnel to deliver the 30 core-sessions of the DPP protocol over 12 mos. Outcomes will be assessed by the research team at the local CES offices at baseline, 3 mos. 6 mos. and 12 mos.

Meets At-Risk Qualification:		
Complete the questions below based on the candidate's responses.		
	Yes - Points	No - Points
Is the candidate a woman who has had a baby weighing more than 9 pounds at birth?	 - 1	 - 0
Does the candidate have a parent with diabetes?	 - 1	 - 0

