Does the candidate have a brother or sister with diabetes?	 - 1	 - 0
Does the candidate weigh as much as or more than the weight listed for their height?	 - 5	 - 0
Is the candidate younger than 65 years of age and gets little or no activity in a typical day?	 - 5	 - 0
Is the candidate between 45 and 64 years of age?	 - 5	 - 0
Is the candidate 65 years of age or older?	 - 9	 - 0
Total Risk Score (score must be 9 or greater to qualify for enrollment in 'At-Risk' category):		

Participants/Recruitment: Men and women (n=15 per arm) who satisfy the inclusion/exclusion will be recruited through local physician's offices, social media, KSRE offices, marketing/listservs, and local businesses. Interested potential participants will fill out an initial eligibility questionnaire via website or over the phone with a study team member. If they pass the screening, a consent session will be scheduled over the phone or over Zoom. The consent form will be emailed to participants prior to the consent session so ensure understanding of the study. The participant will have the option to sign the consent form and email it to the study coordinator or sign the consent form in REDCap.

Inclusion/exclusion criteria. *Inclusion:* 1) Prediabetes as defined as A1C = 5.7-6.4%, fasting glucose = 100-125 mg/dl, (confirmed from physician/medical record in the previous year), history of gestation diabetes mellitus OR a positive result based on the CDC- DPP screener (see figure), 2) Age ≥ 18 yrs., 3) Willing to commit to participate on a weekly basis for the 6 month intervention, 4) Living in the county of a rural KSRE local unit. Rural counties will be defined using the American Community Survey definition which categorizes a county as rural if the population is $< 65,000$ (23), 5) Internet access and capability to use Zoom, 6) Clearance from primary care physician and 7) Access to a scale. *Exclusion.* 1) Diagnosis of T2D, 2) Unable to participate in physical activity.

Randomization: Two rural KSRE local units will be randomized in a 1:1 ratio to either DPP-FB or DPP-R.

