Intervention overview: The DPP is an evidenced based lifestyle intervention based on Social Cognitive Theory which includes topics on nutrition and physical activity in addition to behavior change strategies such as self-monitoring, environmental control, positive reinforcement and accountability (24). Six-month weight loss and physical activity goals, i.e. following completion of the 24-session core curriculum, are 5%-7% and ≥ 150 min/wk. of moderate intensity activity such as brisk walking, respectively. The nutrition portion of the DPP curriculum focuses on reducing fat intake to reduce caloric intake. The physical activity portion of the curriculum focuses on incorporating physical activity throughout the day to reach the goal of 150 min/wk. Increasing lifestyle activities such as taking the stairs, stretching, gardening, and parking further away at the grocery store, etc. are encouraged. At the baseline visit, participants in both

intervention arms will receive a notebook which includes contact information for study personnel, instructions and guidelines for phone calls (DPP-R only), descriptions of the diet and physical activity protocols, handouts/worksheets/assignments specific to each meeting, and charts to self-monitor, weight, physical activity, and fruits and vegetables consumption.

DPP-R intervention delivery. Weekly 60 min. group meetings (12-15 participants) will be held by Zoom over 6 months followed by monthly 60 min. group meetings for the later 6 months. Approximately 5 min prior to the meeting time (typically early evening) participants will receive call in information to join the group meeting by video conferencing or phone.

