shown to provide valid and reliable assessments of PA in adults. Participants will wear the ActiGraph on a belt over the non-dominant hip at the anterior axillary line during waking hours for 7 consecutive days, except for bathing, swimming, and contact sports. A 7-day monitoring period provides a reliable estimate of moderate-to-vigorous PA. ActiGraph data, aggregated over 1-min epochs, will be processed using the protocol used for adults in the 2003-2004 and 2005-2006 cycles of NHANES using the following intensity cut-points: sedentary (< 1.0 METs \leq 100 counts/min), light (METs 1.1-2.99; 101-2019 counts/min.), moderate (METs 3.0-5.99; 2020-5998 counts/min) and vigorous (\geq 6 METs; \geq 5999 counts/min). ActiGraphs will be given to participants during outcomes testing with a prepaid envelope to mail back to the investigators after wearing for 7 days. Participant retention/program attendance. Lifestyle coaches in both intervention arms will maintain records of participant retention and program attendance. Retention will be defined as attendance at 6 mo. and 12 mo. outcome testing. Program attendance will be defined as being present as the beginning and end of the class/call and reporting weekly data.

End study survey. At the end of the 6 mo. intervention, a survey will be conducted to ask about your experience with the program.

Focus group. At the end of the 6 mo. intervention, a recorded focus group will be conducted in all participants to gather information on the overall ease and enjoyment of the program. Questions on barriers to healthy eating and physical activity, time commitment, recommending the program to friends/family,

Statistical analysis & Data management: Baseline measures and demographic characteristics will be summarized for the complete sample using means and standard deviations for continuous variables and frequencies and percentages for categorical variables. Weight loss will be calculated as the difference in body weight between baseline and 6 months. All analyses will be conducted using SAS 9.4 (SAS Institute, Cary, NC). We will compare change in body weight and MVPA between groups at 6 mos. and 12 mos. by using a two-sample t-test. Feasibility will be calculated as the percentage of participants who attended $>$ 75% of the scheduled sessions. We will also conduct a qualitative analysis of focus group and end study surveys to gain insight on the acceptability and enjoyment of the program and suggestions for improvement.

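### With one local unit randomised to each arm, the participant-level t-test cannot separate delivery format from local unit, primary coach or group

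*Combined protocol and SAP*

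**What the plan says.** Three places agree on the design: Specific aims, Design overview and Randomization. The last states that "Two rural KSRE local units will be randomized in a 1:1 ratio to either DPP-FB or DPP-R". Participants/Recruitment sets 15 participants per arm. The inclusion criteria require residence in a county served by a rural local unit, and the Design overview explains that "The KSRE maintains local units which are comprised of single counties or multi-county districts".

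On delivery, Specific aims says "Our research team will train 2 professional staff from KSRE", and the section on lifestyle coaches has a primary coach chosen at the randomised offices. Under Intervention fidelity, a secondary coach or the study coordinator serves only as a substitute. For DPP-R, "Weekly 60 min. group meetings (12-15 participants) will be held by Zoom over 6 months". DPP-FB is described as one coach-moderated Facebook group.

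The primary aim is a between-arm comparison with a stated direction: "We expect greater weight loss and MVPA in the DPP-R arm compared with the DPP-FB arm". The secondary aim has its own: "We expect greater participant retention and program attendance in the DPP-R arm compared with the DPP-FB arm". The analysis section says "We will compare change in body weight and MVPA between groups at 6 mos. and 12 mos. by using a two-sample t-test". Nowhere do the documents mention clustering, an ICC, a site or coach effect, or the limitation that follows from having one unit per arm.

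**The concern.** The t-test treats 30 participants as if each had been randomised independently. In fact two local units were randomised, and a participant's arm follows from the unit to which he or she belongs. Two units can differ in their populations, local resources, coach skill and group dynamics. Any of these could produce a significant difference in weight or MVPA change with no effect of format.

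This bears on the primary aim, because the t-test is the only inferential method named for it. It also bears on what comes next. Specific aims presents the study as the source of pilot data for a "larger, adequately powered trial comparing the effectiveness of remote and Facebook group delivery of DPP". A difference between two places, read as a difference between two formats, would carry into the planning of that trial. The secondary-aim comparison of retention and attendance is confounded in the same way, although no test is planned for it.

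**Working it through.** **Inputs from the documents.** Units randomised: 2, one per arm. Participants per arm: m = 15, so 2 × 15 = 30, which matches the total in Specific aims. DPP-R group size: 12 to 15. Analysis: two-sample t-test on change. The plan gives no power calculation, so it has no figure to reproduce.

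**Assumptions.** Two-sided 5% level, no format effect, and ICCs (of change) of 0.01 to 0.20. The calculation is repeated at m = 12, the lower end of the stated group size.

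**Step 1: is the t-test at participant level?** It must be. A t-test on one unit mean per arm has 2 − 2 = 0 degrees of freedom. With two units there are only two possible allocations, so the smallest two-sided permutation p-value is 1.0. The participant-level test claims 2m − 2 = 28 degrees of freedom.

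**Step 2: how many groups per arm?** Splitting 15 people into two groups would give 7 or 8 in each, below the stated 12 to 15. DPP-R is therefore one group, and DPP-FB is described as one. Two staff for two offices is naturally read as one primary coach per arm. Unit, primary coach and group then all coincide with arm.

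**Step 3: effect on type I error.** Let s² be the total variance of change. With one cluster of m per arm:

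- true variance of the difference = (2s²/m)[1 + (m − 1)ICC]
- variance the pooled t-test estimates, on average = (2s²/m)(1 − ICC)

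Under no format effect the statistic is therefore distributed as k × t with 2m − 2 degrees of freedom, where k = √{[1 + (m − 1)ICC]/(1 − ICC)}. The true type I error is P(|t| > critical value/k). The |t| needed for a true 5% level is k × critical value.

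Example, m = 15 and ICC = 0.05: k = √(1.70/0.95) = 1.338, and the |t| needed is 2.048 × 1.338 = 2.74.

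| ICC | k (m = 15) | Type I error | \|t\| needed | k (m = 12) | Type I error | \|t\| needed |
|---|---|---|---|---|---|---|
| 0 | 1.000 | 5.0% | 2.05 | 1.000 | 5.0% | 2.07 |
| 0.01 | 1.073 | 6.7% | 2.20 | 1.059 | 6.3% | 2.20 |
| 0.05 | 1.338 | 13.7% | 2.74 | 1.277 | 11.9% | 2.65 |
| 0.10 | 1.633 | 22.0% | 3.35 | 1.528 | 18.8% | 3.17 |
| 0.20 | 2.179 | 35.5% | 4.46 | 2.000 | 31.1% | 4.15 |

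Critical values are 2.048 (28 df) and 2.074 (22 df). Simulation with 200,000 trials per cell agreed with the type I errors to within 0.002. The error reaches 10% at an ICC of 0.029 (m = 15) or 0.037 (m = 12).

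**Step 4: would more participants or a unit term help?** No. As m grows, the standard error of the difference cannot fall below √(2 × ICC) SD, which is 0.14 SD at an ICC of 0.01 and 0.45 SD at 0.10. A unit term cannot be fitted, because unit and arm are the same variable.

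**The case against.** The strongest reply is that this is a 30-person pilot with no stated alpha, power calculation or go/no-go rule tied to a p-value, so little depends on the test. That lowers the immediate consequence. It does not make the test valid, because the between-arm comparison is the primary aim and has a predicted direction.

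Several other points stand in part:

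- The ICCs are assumed. The relevant one is the ICC of change from baseline, which removes stable differences in level between units. At 0.01 the inflation is small. But its value is unknown and these data cannot estimate it.
- Coach training, the skills checklist and fidelity review may reduce coach variation, and outcomes are measured by the same research staff with a specified calibrated scale. None of this separates unit or coach from format.
- One primary coach per arm is a reading of the text, not a statement in it. The confounding with local unit does not depend on it.
- The t-test can be read as comparing these two programmes as delivered in these two places. That is fair, but the aims are worded as a comparison of formats.
- For retention and attendance, the analysis section names no between-arm test, so only the wording of the aim and a caveat remain to be settled.

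**Conclusion.** The concern holds and should be fixed before the analysis. Delivery format is fully confounded with local unit: there are 0 degrees of freedom at the randomised level, whatever ICC or significance level is assumed. On the natural reading it is also confounded with primary coach and group. As a test of format, the planned t-test has its nominal error rate only if variance between units is zero. The inflation in the table is illustrative and rests on the assumed two-sided 5% level and ICCs: with 15 per arm, from 6.7% at an ICC of 0.01 to 35.5% at 0.20. Descriptive, feasibility and qualitative results remain usable.

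**What to change.** **In Statistical analysis & Data management**
- Replace the between-arm t-tests at 6 and 12 months with each arm's mean change, SD and 95% confidence interval for weight and MVPA.
- Label these as site-specific estimates in which format, local unit and coach cannot be separated. State that the intervals reflect variation between participants within one unit only.
- If a between-arm difference is still shown, call it exploratory and accompany it with a sensitivity table over assumed ICCs, for example 0.01 to 0.20.

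**In Specific aims**
- Reword the primary aim and its directional expectation to match.
- Present retention and attendance descriptively, with the same caveat.

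**Cost.** No extra participants or visits. The aims and analysis text must be amended, and the sponsor gives up a p-value that could not support a conclusion about format.

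Randomising individuals, stratified by local unit, would remove confounding with unit only. Coach and group would still be one per arm, and there would be some risk of contact between arms, so it is a trade-off and not a full remedy. For the larger trial, several units per arm are needed. With 2, 3 or 4 units per arm the smallest two-sided p-value from an unmatched permutation test is 2/6 = 0.333, 2/20 = 0.100 or 2/70 = 0.029, so at least 4 per arm are required before such a test can fall below 0.05.

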DPP-FB intervention delivery. Formal meetings will not be scheduled. Logistics. Participants will be asked to join a *secret*, lifestyle coach moderated, Facebook® group. The content in a *secret* Facebook® groups is accessible only to invited members, and the existence of the page is hidden from the public. Participants with existing Facebook® accounts will be advised on adjusting privacy settings to control access by other members of their *secret* Facebook® group. Participants will access Facebook® with the iPad provided using Wi-Fi, thus participant's personal data plans will not be impacted. The lifestyle coach will post new modules of the Prevent T2 curriculum to Facebook® weekly over months 1-6 (modules 1-24) and monthly over months 7-12 (modules 25-30). New modules will be posted prior to 9 a.m. on Mondays. De-identified individual participant self-monitoring data (diet, PA, weight loss) and a brief comment from the lifestyle coach regarding the performance of the group will be posted on Tuesday a.m. This allows participants to assess their progress relative to others in the group. Brief discussion points such as "what strategies to increase your level of PA will you try this week?" will be posted on Wednesday and Friday AM. These posts are designed to reinforce the primary objectives of each module and to facilitate inter-participant discussion around these topics. Participants will be asked to comment on each of the discussion point posts. The lifestyle coach will monitor the responses to the discussion point posts daily and will answer questions and/or correct any misinformation that may be included in participant posts. The Friday morning post will include a reminder to sync self-monitoring devices by midnight on Sunday. New posts will be "pinned" to the top of the wall and included in the "announcements section", to ensure the new posts are easily identified. Participant engagement, which will be tracked across the 6-mo. trial, can take the form of "liking" or "commenting" on the posts, or contributing new posts. Lifestyle coaches will monitor the Facebook® group on the Monday following the posting of a new curriculum module to determine if the module has been accessed. This is analogous to attendance in the Zoom® group. Lifestyle coaches will send email reminders to participants who do not access 2 consecutive module postings. Participants will be encouraged to contact lifestyle coaches with any questions that arise during the intervention using Facebook® messenger, which automatically alerts lifestyle coaches that a message has been received.

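### Baseline MVPA is recorded in the week after both arms receive the activity protocol and charts; completing the wear week first would be a cheap, minor-priority improvement

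*Combined protocol and SAP*

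**What the plan says.** The Physical activity paragraph under Outcome Assessments sets a wear period of 7 consecutive days and fixes when it starts: "ActiGraphs will be given to participants during outcomes testing with a prepaid envelope to mail back to the investigators after wearing for 7 days". The opening of Outcome Assessments places testing at the local extension unit at baseline, 3, 6 and 12 months.

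The Intervention overview says when the notebook is issued: "At the baseline visit, participants in both" arms receive it. Its contents include "contact information for study personnel, instructions and guidelines for phone calls (DPP-R only), descriptions of the diet and physical activity protocols" and "handouts/worksheets/assignments specific to each meeting, and charts to self-monitor, weight, physical activity". The same section counts self-monitoring among the program's active components: "behavior change strategies such as self-monitoring, environmental control, positive reinforcement and accountability".

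The Self-monitoring section provides a Fitbit for steps but gives no date of issue. Delivery is weekly in both arms. For DPP-R, "Weekly 60 min. group meetings (12-15 participants) will be held by Zoom over 6 months"; for DPP-FB, "New modules will be posted prior to 9 a.m. on Mondays". Neither section dates the first meeting or module relative to baseline testing.

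The primary aim compares weight and MVPA between arms. The statistical section names one MVPA analysis, a two-sample t-test of change between groups at 6 and 12 months.

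**The concern.** A change score needs a baseline that precedes the intervention. Weight has one, because it is measured at the visit itself. MVPA does not have one on the stated order: the device is handed over at testing, and the following week supplies the baseline. During that week participants already hold a description of the activity protocol and charts for tracking their own activity, and tracking is something the program itself uses to change behavior.

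If some participants respond to the material straight away, their baseline MVPA is too high and their change too small. The week cannot be collected again once the program is running. The study is meant to supply pilot data for a larger, adequately powered trial, so the arm-level MVPA changes may be carried forward into that planning even though the plan tests only the difference between arms.

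**Working it through.** The plan gives no figure to reproduce here. The check is one of timing, followed by the algebra of a change score.

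**Order of events**

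1. Device handed out: during outcomes testing (Physical activity).
2. Wear: the 7 days after hand-out, then return by mail (same paragraph).
3. Activity protocol and charts handed out: at the baseline visit, both arms (Intervention overview).
4. Steps 1 and 3 fall on the same occasion if the baseline visit is baseline outcomes testing. The plan does not say so outright, but it describes no other baseline visit.
5. On that reading, the materials are in hand for the whole baseline wear week.
6. Fitbit, first session, first module: undated. The wording in the coach-training section about events before the intervention begins concerns training of coaches only. Nothing places these items inside the wear week, and nothing keeps them out.

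**Effect on the estimates**

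Let D_R and D_FB be the true mean changes in MVPA, and c_R and c_FB the mean rise in the baseline week caused by early exposure.

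- Observed change in an arm = D − c, so a descriptive within-arm change is understated by c.
- Observed between-arm difference = (D_R − c_R) − (D_FB − c_FB) = (D_R − D_FB) − (c_R − c_FB).
- Bias in the t-test contrast = −(c_R − c_FB), which is 0 when c_R = c_FB.

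The documents give no value for c. To show the pattern only, assume true changes of 60 (DPP-R) and 30 (DPP-FB) min/wk, a true difference of 30:

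- Rise of 15 in both arms: changes 60 − 15 = 45 and 30 − 15 = 15; difference 30, unchanged.
- Rise of 15 in DPP-R only: changes 45 and 30; difference 15.
- Rise of 15 in DPP-FB only: changes 60 and 15; difference 45.

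These are assumed inputs, not estimates of what will happen.

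**Which case do the documents suggest?** The notebook reaches both arms at the same point, and the only stated difference in its content is the call instructions for DPP-R. For the one exposure that the text does place at baseline, roughly equal rises are the reasonable expectation.

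**The case against.** The strongest reply is that no harm to the planned analysis is shown. The only MVPA test is between arms, the notebook's activity content is common to both, and a common rise cancels. No within-arm analysis is planned. This stands, and it is why the priority is minor.

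Some text also makes early use less likely. The handouts are tied to particular meetings, and participants enter their data in the intervals between weekly meetings, so scheduled monitoring appears to follow the sessions. This stands in part: the activity protocol and the charts are listed separately from the meeting handouts, and nothing asks participants to leave them unopened.

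There is also proportion. Each arm is a single extension unit, so any MVPA difference is already inseparable from site. With 15 per arm, the detectable difference is about 1.06 SD (two-sided 5% and 80% power, both assumed because the plan states neither). A one-week effect of unknown size, probably shared, is second-order beside that. This stands too.

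A reader might infer more: that the intervention is already running during the baseline week, or that the comparison of arms is biased. The documents support neither. The first session, first module and Fitbit are undated, and silence is not evidence of overlap. Nor would counting the meetings or posts that could fall in one week supply a magnitude, since such a count says nothing about minutes of MVPA.

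**Conclusion.** The point holds as a cheap improvement of minor priority. On the stated order, baseline MVPA, part of the primary aim, is recorded after the activity protocol and activity charts have been issued to both arms. This rests on reading the baseline visit as baseline outcomes testing.

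Whether participants act on the material in that week is a risk, not something that the documents show, and its size and sign are unknown. The main exposure is to reported arm-level change in MVPA, understated by whatever rise occurs. The between-arm t-test is affected only to the extent that the rise differs by arm. Baseline weight is not affected.

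**What to change.** State the order in the protocol, in one or two sentences. There are two ways to do it:

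- **Delay the materials.** Schedule baseline testing at least 7 days before the group's first session or module. Issue the activity protocol, activity charts and Fitbit only when the 7-day baseline wear is complete. Contact information and call instructions can still be given at the visit. The cost is about a week between baseline weight and the start of the intervention, and a second delivery of materials.
- **Move the wear earlier.** Mail the ActiGraph after the remote consent session, so that wear ends before the baseline visit and the whole notebook can be given there as planned. The first session or module then follows that visit. The cost is remote wear instructions, consent at least a week before the visit, and one mailing per consented person. That is 15 × 2 = 30 if everyone consented is enrolled, and more if some are not: physician clearance is required, and the plan does not say whether it is obtained before or after consent.

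The first option keeps device hand-out in person; the second keeps the notebook in one piece and need not widen the gap after baseline weight. Either gives a baseline MVPA value that precedes the activity materials and the program.
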